Exclusion Criteria	
 1. Coagulopathy (i.e., international normalized ratio >2.0, activated partial thromboplastin time >50 seconds or platelet count <50,000/mm³) 2. Known bleeding disorder 3. Clinically relevant bleeding as defined by the International Society on Thrombosis and Hemostasis (i.e., Hb decreased ≥2 g/dl in 24 hours, required medical or surgical intervention to restore hemostasis, or in a critical organ system [i.e., retroperitoneum, pulmonary, intracranial or central nervous system]) 4. Admitted for trauma, or neurologic or spine surgery) 5. <60 days from a clinically relevant bleeding as defined above 6. <7 days after trauma or surgery 7. Anticipated surgery within 48 hours after insertion of the CVC 8. Renal failure (i.e., creatinine clearance <30 mL/min) 9. Presence of epidural catheter 9. Currently taking an antithrombotic agent (e.g., LMWH, UFH at therapeutic doses, Coumadin or aspirin) 10. Radiologically documented DVT at the site of insertion of the CVC in the previous 6 weeks 11. Known hypersensitivity to heparin or its components, including pork products 12. History of HIT (i.e., positive serotonin release assay)

	13. Currently pregnant 14. Currently lactating 15. Prior enrollment in the study 16. Limitation of care
Treatment Plan	Eligible subjects will be randomized 1:1 to treatment or control. In subjects randomized to treatment, noxaparin will be given within the first 24 hours after CVC insertion and then every 12 hours (+/-2 hours) thereafter until removal of the CVC. Dosing will start at 0.75 mg/kg for children \leq 2 months old or 0.5 mg/kg (maximum of 30 mg) for older children and will be titrated to a target anti-Xa activity of 0.2-0.5 IU/mL. Safety assessments for bleeding will be completed daily. In subjects randomized to control, no placebo will be given.

STUDY SCHEMA

LIST OF ABBREVIATIONS

AE – adverse event
CADVT – catheter-associated deep venous thrombosis
CAT - Calibrated Automated Thrombogram
Co-I – co-investigator
CRF – case report form
CVC – central venous catheter
DSMB – data and safety monitoring board
DVT – deep venous thrombosis
EDTA – ethylenediaminetetraacetic acid
ETP – endogenous thrombin potential
FDA – Food and Drug Administration
Hb – hemoglobin
HIPAA – Health Insurance Portability and Accountability Act
HIT – heparin-induced thrombocytopenia
ICU – intensive care unit
IL – interleukin
IP – Investigational Product
IRB – institutional review board

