Subjects randomized to the treatment arm will receive enoxaparin adjusted to the target anti-Xa activity. Subjects randomized to the control arm will not receive placebo because of ethical concerns of inducing pain with subcutaneous administration without any potential for direct benefit. All subjects in the study will undergo the remaining study procedures.

TREATMENT REGIMEN WITH ENOXAPARIN

The 1st dose of enoxaparin be given <24 hours after insertion of the CVC. The initial dose will be 0.75 mg/kg for children ≤2 months old or 0.5 mg/kg (maximum of 30 mg) for older children (Table 1). The initial dose will be doubled in obese children (refer to Appendix I and II) and halved in children with renal insufficiency (estimated creatinine clearance calculated by the Schwartz equation $<75 \text{ mL/min/1.73 m}^2$).⁴⁹ The clinical nurse will give enoxaparin subcutaneously every 12±2 hours after the first dose until removal of the CVC, or earlier upon discharge from the ICU, radiologic diagnosis of CADVT, start of therapeutic anticoagulation, clinically relevant bleeding develops, HIT is diagnosed, or 28 days after insertion of the CVC.

Administration

Route. Enoxaparin is to be administered by subcutaneous route per local site clinical procedures.

Site. In children <10 kg or <1 year of age, the thigh is the preferred site of administration. Alternate between the left and right thigh. In children ≥10 kg or ≥1 year of age, the abdomen is the preferred site. For children who do not have sufficient subcutaneous tissue in the abdomen, the anterolateral thigh may be used as secondary site for administration.

Table 1: Initial dose

Age	Drug	Dose/ Potency*	Dose Frequency	Route	Regimen/ Treatment Period†	Use
Children ≤2 mos.	Enoxaparin	0.75 mg/kg	Q12 hours	Subcutaneous	Until CVC is removed	Experimental
Children >2 mos.	Enoxaparin	0.5 mg/kg (maximum of 30 mg)	Q12 hours	Subcutaneous	Until CVC is removed	Experimental

*The initial dose will be doubled in obese children (refer to Appendix I and II) and halved in children with renal insufficiency (estimated creatinine clearance calculated by the Schwartz equation $<75 \text{ mL/min/1.73 m}^2$).⁴⁹ †Enoxaparin treatment will stop before the CVC is removed upon discharge from the ICU, radiologic diagnosis of CADVT, start of therapeutic anticoagulation, clinically relevant bleed develops, HIT is diagnosed, or 28 days after insertion of the CVC, whichever comes first.

Titration dose

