An adverse event is defined as any untoward medical occurrence in a patient or clinical investigation subject administered a pharmaceutical product and which does not necessarily have to have a causal relationship with this treatment. An adverse event can therefore be any unfavorable and unintended sign (including an abnormal laboratory finding, for example), symptom, or disease temporally associated with the use of a medicinal product or protocol-specified procedure, whether or not considered related to the medicinal product or protocol-specified procedure. Any worsening (*i.e.*, any clinically significant adverse change in frequency and/or intensity) of a preexisting condition that is temporally associated with the use of enoxaparin is also an adverse event.

Adverse events may occur during the course of the use of the IP in clinical trials or within the follow-up period specified by the protocol, or prescribed in clinical practice, from overdose (whether accidental or intentional), from abuse and from withdrawal.

Serious adverse event. A serious adverse event is an AE occurring during any study phase (*i.e.*, treatment, follow-up), that fulfills one or more of the following criteria:

1. Results in death
2. Is immediately life-threatening
3. Requires in-patient hospitalization or prolongation of existing hospitalization
4. Results in persistent or significant disability or incapacity
5. Results in a congenital abnormality or birth defect
6. Is an important medical event that may jeopardize the subject or may require medical intervention to prevent one of the outcomes listed above

Each AE will be graded for severity per the NCI CTCAE version 4.0, and these criteria must be used in grading the severity of AEs. The criteria can be found at:

<http://ctep.cancer.gov/reporting/ctc.html>

For those AEs, which are not listed as part of the NCI CTCAE version 4.0, the same grading system should be used, where:

- **Mild** corresponds to an event not resulting in disability or incapacity and which resolves without intervention
- **Moderate** corresponds to an event not resulting in disability or incapacity but which requires intervention
- **Severe** corresponds to an event resulting in temporary disability or incapacity and which requires intervention
- **Life-threatening** corresponds to an event in which the patient was at risk of death at the time of the event
- **Fatal** corresponds to an event that results in the death of the patient

AE Expectedness

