site investigators within 15 calendar days.

A safety monitor is responsible for ongoing timely monitoring of reports of all SAEs submitted by site PIs, or other sources to ensure high-quality reporting, good clinical care and to quickly identify safety concerns. The identification of SAEs will begin when a member of the local research team reports an adverse event. The local research team will monitor each child daily for pre-defined adverse events, particularly clinically relevant bleeding. The research team will interview the clinical team and review the medical records daily for these events. The site PI or his/her designee will conduct prompt investigations of all reported adverse events, especially bleeding. All SAEs will be documented on a SAE form, entered in OnCore and communicated to the PM as soon as possible and <24 hours of the site PI knowing the event.

SAEs will be reported to the Yale Human Investigation Committee and the IRBs of the participating sites per policy.

Adverse Event Committee (AEC)

PI [name] will assemble an independent 3-member AEC composed of a pediatric hematologist (chair), a pediatric intensivist and a nurse. The responsibility of the AEC is to classify all AEs for publication and presentation purposes.

Minimizing Risks

To minimize the risk of bleeding, we will exclude children at high risk of bleeding. Enoxaparin will be held immediately and permanently after a clinically relevant bleeding event as defined by the International Society on Thrombosis and Hemostasis.⁵² Bleeding from enoxaparin can be reversed with protamine or administration of fresh frozen plasma. See section on Holding the Dose, which contains criteria for holding enoxaparin temporarily and when to restart the drug. Enoxaparin will not be replaced with another agent while the drug is on hold.

Platelet count will be monitored for the development of HIT. Enoxaparin and all heparin-related products will be held temporarily for unexplained decrease in platelet count.^{14, 53} Enoxaparin will not be restarted until the child tests negative for HIT.

Subcutaneous administration of enoxaparin may cause pain. As per local ICU practice, enoxaparin may be given through a subcutaneous catheter.

It is unlikely that the blood draws will result in anemia. Packed red blood cells can be transfused for anemia per the direction of the clinical team.

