Meeting format. The DSMB will meet as often as needed but the minimum will be at least once before the start of enrollment, after 10, 25 and 50 children have been enrolled, and after enrollment is completed (100 children enrolled). The DSMB will monitor the study according to guidelines specified in the research protocol and the operating procedures established at the initial meeting, unless the DSMB determines during the course of the study that modification of the guidelines is in the best interest of the study or the children in the study. The DSMB chair will set the meeting agenda. The DSMB members, the study statistician, project manager and the Sponsor PI will attend the session, at which time data concerning study conduct and aggregate safety data are discussed. Minutes of the meeting will be taken by staff of the DSMB.

Interim data summary reports. The study statistician will prepare data summary reports and send these directly to the DSMB members and the study team ≥ 7 days prior to the meeting. The report will focus on patient enrollment and demographics, data completeness, other study performance measures, and rates of serious adverse events. In addition to reports prepared by the statistician, PI [name] may prepare a report addressing concerns he anticipates the DSMB will have regarding the conduct of the study.

Communication of DSMB recommendations. At the conclusion of each DSMB meeting, the DSMB will provide a verbal report to PI [name] indicating areas of concern regarding performance and safety. Soon after the meeting, the chair will provide a written report to PI [name], including a summary of the DSMB's recommendations. In addition, the chair will provide a memorandum to PI [name] (including date of the meeting, a listing of data reviewed, recommendations, and date of

next review). PI [name] will forward this promptly to each participating site for submission to their IRBs, including the Yale Human Investigation Committee and the Project Management team.

The DSMB has the authority to recommend that the study protocol be terminated, temporarily suspended, or amended. This recommendation will be discussed with PI [name] before any action is taken. If the DSMB recommends a protocol amendment, the Yale Human Investigation Committee and site IRBs must approve the amendment before it is implemented.

Quality Management / Monitoring

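### The only explicit rule on worsening of a pre-existing condition is tied to enoxaparin, so whether worsening counts as an AE in control children is left to each site's reading

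*Combined protocol and SAP*

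**What the plan says.** The Definition section builds an AE from three sentences. The first refers to "any untoward medical occurrence in a patient or clinical investigation subject administered a pharmaceutical product". The second takes in any unfavorable sign, "symptom, or disease temporally associated with the use of a medicinal product or protocol-specified procedure", whether or not it is thought related. The third deals with conditions present at entry: clinically significant worsening "of a preexisting condition that is temporally associated with the use of enoxaparin is also an adverse event".

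The SAE definition rests on the AE definition: "A serious adverse event is an AE occurring during any study phase" that meets one of six seriousness criteria.

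On control exposure, the Randomization section states: "Subjects randomized to the control arm will not receive placebo". The Treatment Plan in the Trial Summary says the same.

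Two later uses of these counts matter. The statistician's interim report to the DSMB covers, among other items, "other study performance measures, and rates of serious adverse events". The independent Adverse Event Committee is to "classify all AEs for publication and presentation purposes".

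**The concern.** The children are enrolled because they are critically ill, so deterioration of the illness they arrived with is a natural source of AEs and SAEs. The one sentence that addresses it names a drug that only one arm receives. A site following the text closely has an explicit instruction to log worsening in a treated child and no matching instruction for a control child. With no placebo, the staff who decide what to log know the arm.

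At stake are the overall AE and SAE counts. If worsening is logged more readily in the enoxaparin arm, that arm will look worse on total events for a reason unrelated to the drug. An excess produced this way could not be separated afterwards from a real one, because events that were never logged are hard to recover.

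**Working it through.** The protocol gives no expected AE or SAE rate by arm, so there is no figure of its own to reproduce. The main check is of the text.

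**Step 1. Can worsening in a control child meet each sentence?**

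| Sentence | Exposure it requires | Control child |
|---|---|---|
| First general sentence | A pharmaceutical product | Possibly, if other ICU medicines count; the text does not say |
| Second general sentence | A medicinal product or a study procedure, linked in time | Possibly, if the worsening falls near one |
| Worsening sentence | Enoxaparin | No |
| SAE | Must first be an AE | Inherits the answers above |

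**Step 2. Does any other section give a rule for controls?** None defines worsening for them. Procedure for Reporting Adverse Events and the Trial Flow Chart say when AEs are recorded and how often they are assessed. They do not say what counts as one.

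**Step 3. Which outputs depend on the sentence?** The safety outcomes in Outcome Measures are clinically relevant bleeding, confirmed HIT and mortality. The trigger in Minimizing Risks is 5 or more clinically relevant bleeds. Each has its own definition and none uses the worsening sentence. What remains exposed is the total AE and SAE count.

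**Step 4. How large could it be?** The following are assumptions, not document figures:
- The true event rate per child, λ, is the same in both arms (no drug effect).
- A share w of events is worsening of a pre-existing condition.
- All worsening is logged in the treated arm. A fraction c of it is logged in controls through the general sentences.

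Recorded rate, treated: λ. Recorded rate, control: λ[1 − w(1 − c)]. Ratio = 1/[1 − w(1 − c)].

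| w | c = 0 (all missed) | c = 0.5 | c = 1 |
|---|---|---|---|
| 10% | 1/0.90 = 1.11 | 1/0.95 = 1.05 | 1.00 |
| 25% | 1/0.75 = 1.33 | 1/0.875 = 1.14 | 1.00 |
| 50% | 1/0.50 = 2.00 | 1/0.75 = 1.33 | 1.00 |

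The c = 0 column is the upper bound 1/(1 − w). These are ratios of event counts. The proportion of children with at least one event would move less, because a control child with some other logged event is still counted.

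**The case against.** The strongest reply is that the worsening sentence adds to the definition and does not restrict it, since it says *also*. The sentence before it already reaches control events close in time to a study procedure. Controls undergo every procedure except enoxaparin: correlative blood draws within 24 hours of catheter insertion, about 24 hours later, at day 4 and at the end of study, plus safety laboratory tests, limb examination and ultrasound. Mean catheterization in the investigators' earlier cohorts was 6 days, so much control-arm deterioration would fall near a procedure.

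Other sections also show that collection in both arms is intended. AEs are recorded from the signing of permission, before any dose. Each child is monitored daily. The flow chart limits enoxaparin to the treatment arm but not AE assessment. AE Expectedness treats natural progression of underlying disease as a question of expectedness. AE Attribution treats a documented pre-existing condition as a reason to rate an event unrelated. Both presuppose that such events have already been logged.

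Finally, no comparison of overall AE or SAE rates is planned, and the interim report section does not say that SAE rates are shown by arm.

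Most of this stands. It rules out reading the sentence as a deliberate one-arm counting rule, and it limits the likely size. It does not close the gap. Evidence of intent does not change the operative definition, and worsening that is not close to a procedure still depends on a site's choice. The expectedness and attribution sections support the remedy: progression should be logged first and classified afterwards. If the DSMB sees pooled rates, missed control events would understate the total instead of tilting the comparison.

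**Conclusion.** The wording is asymmetric and should be corrected. Worsening is explicitly an AE, and so potentially an SAE, in the treated arm. In the control arm it depends on how each of six sites reads the general definition. With allocation known, this permits differential recording, and any resulting tilt in total AE and SAE counts would run against enoxaparin.

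A reader might infer more: that the same death or prolonged stay from underlying illness is an SAE in one arm and cannot be one in the other, or that the planned safety comparison is compromised. The documents do not support either. The general sentences can capture control events, two-arm collection is clearly intended, and the named safety outcomes and bleeding trigger are untouched.

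The size cannot be estimated from the protocol. The ratio of 1/(1 − w) assumes that every worsening event in controls is missed and none in the treated arm, with w itself assumed. It is a ceiling at each w, not a forecast.

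**What to change.** Reword the Definition section so that an AE is any untoward medical occurrence in a randomised child in either arm, whether or not enoxaparin was given, including clinically significant worsening of a pre-existing condition during study participation. Remove the link to enoxaparin as a condition for counting an event and keep it in the attribution field only. State that AEs and SAEs will be tabulated by randomised arm regardless of attribution. Because the current recording window closes 30 hours after the last enoxaparin dose, which a control child does not have, the period of participation needs an end that applies to both arms.

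The cost is one reworded definition in an amendment and a note in site training. Sites would log somewhat more AEs in about 50 control children (100 randomised 1:1), who are already assessed daily. No visits, procedures or patients are added. The change works best if made prospectively.
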